5.2 Drug/Device Handling: n/a

5.3 Biosafety: n/a

5.4 Stem Cells: n/a

## 6.0 Procedures Involved

6.1 Study Design: This is a prospective study

Study Procedures: All patients who are enrolled in our TSA or RCR studies fit the criteria of being scheduled for overnight shoulder surgery and having an ISB with or without LB. The patients will already be randomized into either an ISB with bupivacaine or with bupivacaine and LB. If the patient is not enrolled or does not fit inclusion criteria for the RCR or TSA study they will then be randomized to either bupivacaine or liposome bupivacaine ISB. The patients will perform spirometry (one large exhale into a spirometer) and have an ultrasound examination of their diaphragm at baseline prior to the block, in PACU after their procedure, and on postoperative day 1 (24 hours after ISB). Diaphragmatic movement will be evaluated by real-time M-mode ultrasonography of the hemidiaphragm using a 17-mm 1- to 5-MHz broadband phased array US probe. Patients are to be scanned in an upright sitting position and scanned from a low intercostal or subcostal approach using the liver or spleen as an acoustic window. M Mode will be applied and the range of diaphragmatic movement from the resting expiratory position to deep inspiration (sigh test) will be recorded as well as the range of diaphragmatic movement from resting expiratory position when quickly inspiring through the nose (sniff test). This will occur three times, at baseline prior to surgery, in the recovery room, and on the ward on postoperative day 1. All nerve blocks will be confirmed to be functional via a sensory skin test prior to surgery or in the recovery room prior to the recovery room evaluation.

6.2 Study Duration: The patients will be in the study for 2 days. The duration of the study should be 3 months to enroll the 22 patients.

6.3 Individually Identifiable Health Information: PHI will be recorded but once data collection is done then the phi will be removed and replaced with unique identifier. This is just to ensure we see the correct patient for the data collection.

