## 4.0 Study Endpoints/Events/Outcomes

- 4.1 Primary Endpoint/Event/Outcome: The primary study endpoint will be diaphragm excursion (movement in cm) from rest to sigh in a sitting position.
- 4.2 Secondary Endpoint(s)/Event(s)/Outcome(s): The secondary endpoint will be the diaphragm excursion (movement in cm) from rest to a quick inspiratory breath.
- 4.3 Secondary Endpoint(s)/Event(s)/Outcome(s): Evaluation of baseline FEV1, FVC (or FEV6) and FEV1/FVC ratio via spirometry.

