6.4 Use of radiation: n/a

6.5 Use of Center for Magnetic Resonance Research: n/a

## 7.0 Data and Specimen Banking

- 7.1 Storage and Access: the data will be kept in the University box. Data is kept for 7 years.
- 7.2 Data: The data kept will be patient demographics such as weight, BMI, age, sex. Also, block medications and volume used, time of injection, surgical procedure, range of diaphragm movement at baseline, in recovery room, and on postoperative day 1 and spirometry at baseline, in recovery and postoperative day 1.
- 7.3 Release/Sharing: data will be kept with the PI and co-I

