### **15.0 Statistical Considerations**

15.1 Data Analysis Plan: We will use the average of the three US exams for each timed measurement as the definitive measurement. We will also use FEV1, FVC (or FEV6) and FEV1/FVC (or FEV6) ratio for each time period as a secondary measurement. This data will be given to the statistician who will compare those in the LB ISB group to the bupivacaine ISB group to evaluate for differences (if any) between the movement of the diaphragms in each group.

*15.2* Power Analysis: We assumed a 5% rate of block at 24 hours in bupivacaine and a 66% block for liposome bupivacaine. With an alpha of 0.05 and power of 80% we determined we need 9 patients in each group. Assuming we would have 20% patients drop out, screen fail, or discharge early we planned to enroll 11 per group for total of 22 patients.

*15.3* Statistical Analysis: This study will be analyzed by our staff biostatistician. The data will be de-identified and shared with him in box. The statistician will be provided the protocol so they are able to analyze for primary and secondary objectives.

*15.4* Data Integrity: All patients will be assigned a unique patient identifier. The data that will be sent to the statistician will be de-identified.

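### The ultrasound approach is neither held constant within a patient nor listed among the data kept, which adds a modest, avoidable noise to excursion in cm and weakens the baseline scan as a reference.

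*Combined protocol and SAP*

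**What the plan says.** Section 4.1 makes the outcome a distance: "The primary study endpoint will be diaphragm excursion (movement in cm) from rest to sigh in a sitting position". Sections 5.1 and 6.1 describe the scan in the same words, with the patient "scanned from a low intercostal or subcostal approach using the liver or spleen as an acoustic window". Section 6.1 also fixes the sitting position, M-mode, the probe, and the sigh and sniff manoeuvres. It does not say how to choose between the two approaches or that the choice carries over from one scan to the next.

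On timing, section 6.1 states: "This will occur three times, at baseline prior to surgery, in the recovery room, and on the ward on postoperative day 1". Section 5.1 adds a day 2 assessment for patients still in hospital.

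The ultrasound item in the section 7.2 list of data kept is the "range of diaphragm movement at baseline, in recovery room, and on postoperative day 1". Approach, window and side are not in that list.

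For the analysis, section 15.1 says: "We will use the average of the three US exams for each timed measurement as the definitive measurement". I read this as three repeats at each time point, although section 6.1 does not describe repeats. The statistician will then "compare those in the LB ISB group to the bupivacaine ISB group to evaluate for differences (if any) between the movement of the diaphragms". Section 15 does not name change from baseline or adjustment for baseline, and it contains no check on approach.

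**The concern.** M-mode reads motion along the beam. Two approaches that meet the diaphragm at different angles can give different distances for the same movement. The plan allows either approach at any scan, and the scans are made before surgery, in the recovery room and on the ward, so the view may change between visits.

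Three things follow if it does. A day 1 value set against the same patient's baseline mixes a change of view with a change of movement. The average of three exams either carries the changed view in full or blends two views. A comparison of groups at one visit includes a spread between views that has nothing to do with the block. With 9 evaluable patients planned per group, there is little room for noise that can be prevented at no real cost.

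**Working it through.** **The plan's own figure.** Section 15.2 states: "We assumed a 5% rate of block at 24 hours in bupivacaine and a 66% block for liposome bupivacaine". It continues: "With an alpha of 0.05 and power of 80% we determined we need 9 patients in each group". With p1 = 0.05, p2 = 0.66 and mean 0.355, two-sided, pooled variance and no continuity correction:

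n = [1.960 × √(2 × 0.355 × 0.645) + 0.842 × √(0.05 × 0.95 + 0.66 × 0.34)]² / 0.61² = (1.326 + 0.439)² / 0.3721 = 8.4, so 9 per group.

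The figure reproduces, with approximate power of 83.3% at 9 per group. It is a calculation on block rates and says nothing about the spread of excursion in cm.

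**Inputs for the size of the view effect**

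- From section 15.2: blocked share p at 24 hours of 0.05 (bupivacaine) and 0.66 (liposome bupivacaine), and 9 + 9 = 18 evaluable patients.
- Assumed, because the documents give none of these: unblocked sigh mean m and SD s of 4/1.0, 5/1.5 or 6/2.0 cm; excursion of about zero when blocked; one view aligned with the motion and the other off by t = 30 or 45 degrees; half of the day 1 scans from each view, irrespective of arm; a reading equal to cos(t) of the true distance.

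The shortfall of the off-axis view is 1 − cos 30° = 0.134 or 1 − cos 45° = 0.293.

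**Formulas.** Let c = cos(t), k1 = (1 + c)/2 and k2 = (1 + c²)/2; with a single aligned view, k1 = k2 = 1. In each arm:

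- mean = (1 − p) × m × k1
- variance = (1 − p) × (m² + s²) × k2 − mean²

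D is the difference in arm means divided by the square root of the average of the two variances. D0 is D with one view and D1 is D with mixed views. Extra variance relative to the group difference is (D0/D1)² − 1, and the equivalent number of patients is 18 × (D1/D0)². The ratio is the right measure because a short reading shrinks both the difference and the raw variance.

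**One case in full (4/1.0 cm, 45 degrees)**

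- One view: bupivacaine mean 0.95 × 4 = 3.80, variance 0.95 × 17 − 3.80² = 1.71. Liposome bupivacaine mean 0.34 × 4 = 1.36, variance 0.34 × 17 − 1.36² = 3.93. D0 = 2.44/√2.82 = 1.45.
- Mixed views (k1 = 0.854, k2 = 0.75): means 3.24 and 1.16, variances 1.59 and 2.99. D1 = 2.08/√2.29 = 1.38.
- Extra variance 11.4%; 18 patients are worth 16.2.

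**All cases**

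| Mean/SD (cm) | D0 | D1, 30° | Extra | Patients | D1, 45° | Extra | Patients |
|---|---|---|---|---|---|---|---|
| 4/1.0 | 1.45 | 1.44 | 2.0% | 17.6 | 1.38 | 11.4% | 16.2 |
| 5/1.5 | 1.38 | 1.37 | 1.9% | 17.7 | 1.32 | 10.7% | 16.3 |
| 6/2.0 | 1.34 | 1.33 | 1.8% | 17.7 | 1.28 | 10.2% | 16.3 |

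**In terms of power.** Take a comparison that would have 80% power with one view, so that the expected test statistic is 1.960 + 0.842 = 2.80. Dividing by √1.02 gives 2.77 and power of about 79%; dividing by √1.114 gives 2.65 and power of about 76%.

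**The case against.** The best reply is that the effect is small and that much is already standardised: position, mode, probe, manoeuvres and an average of three exams. The either/or wording may simply list the windows needed across different patients, and liver or spleen would be expected to follow the side scanned. Nothing in the documents says that operators switch view within a patient. All of this is fair and keeps the point modest. It does not remove it, because no text excludes a switch, and averaging does not correct a view shared by all three exams.

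A second objection stands in full. Section 15.1 names a comparison between groups, and the figures above describe a mix of views across patients at one visit. Holding the view constant within each patient leaves that mix in place, so it helps only where baseline is used as a reference or where repeat exams are averaged.

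A reader might infer more than the documents support in three ways:

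- **A much larger loss.** If every day 1 scan had full, unblocked movement, the added variance 0.25 × (m × shortfall)²/s² would run from 4% (6/2.0 cm, 30 degrees) to 34% (4/1.0 cm, 45 degrees), and 18 patients would be worth about 17 to 13. That contradicts section 15.2, which expects 66% of one arm to be blocked. A diaphragm that barely moves carries almost no view error.
- **Bias between arms.** That would need the choice of view to differ by arm, and nothing in the documents says that it does. They also do not say whether the person scanning is blinded, so it cannot be ruled out.
- **A switch that could never be traced.** Section 7.2 lists the data kept, but neither the case report form nor the practice for keeping images is in the documents.

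**Conclusion.** The gap is real and its likely effect is modest. The approach is open at every scan, is not tied to the patient, and is not among the data listed as kept. The consequence is some avoidable loss of precision in the primary endpoint and a weaker baseline.

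Its size cannot be derived from the documents. The 2% to 11% rests on the assumed angles, means and SDs, near-zero movement when blocked, and the cosine model. An even mix of views is the worst mix for added variance at a given angle in unblocked patients, so a less even mix would generally do less harm. With a curved diaphragm an oblique beam could over-read instead; that changes the direction of the error but not its dependence on the view. The point does not put the trial's validity in doubt and gives no reason to change the sample size. It is worth acting on because the remedy is almost free and must be in place before the scans are made.

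**What to change.** - **Section 6.1 (and 5.1 to match):** choose one approach per patient at the baseline scan, and use that approach and the operated side for all exams at every later visit, including day 2 where it is done. If the baseline view cannot be obtained later, take the other view, flag it, and keep the value in the primary analysis.
- **Section 7.2:** add approach and side for each exam.
- **Section 15.1:** let the day 1 comparison use the patient's own baseline excursion, for example as a covariate. A baseline taken from the same view carries the same view effect, so adjustment can take out part of the spread between patients. Without this step, most of the benefit of a constant view is not realised in the group comparison.

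A skin mark, a matched operator, or a sensitivity analysis without flagged scans would be optional; with about 9 per group, that last analysis would be weak.

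The cost is a few sentences and two form fields. The downside is that a later scan may take slightly longer to match the baseline view. No visit, treatment or sample size changes.

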6.4 Use of radiation: n/a

6.5 Use of Center for Magnetic Resonance Research: n/a

## 7.0 Data and Specimen Banking

- 7.1 Storage and Access: the data will be kept in the University box. Data is kept for 7 years.
- 7.2 Data: The data kept will be patient demographics such as weight, BMI, age, sex. Also, block medications and volume used, time of injection, surgical procedure, range of diaphragm movement at baseline, in recovery room, and on postoperative day 1 and spirometry at baseline, in recovery and postoperative day 1.
- 7.3 Release/Sharing: data will be kept with the PI and co-I

## **8.0 Sharing of Results with Participants**

- 8.1 No results will be shared with participants.

## **9.0 Study Population**

- 9.1 Inclusion Criteria: All patients age 18 years and older who are scheduled for shoulder surgery with interscalene block and remain in the hospital for more than 24 hours that are being randomized into a bupivacaine versus LB ISB block study or those who are not enrolled in the TSA or RCR study but are having shoulder surgery with ISB and planned to spend one night in the hospital.
- 9.2 Exclusion Criteria: Non-English speaking patients.
- 9.3 Screening: On the week to day prior to surgery patients will be identified from surgical case list. Then prior to or on day of surgery patients will be asked to participate in the study and given enough time to decide to participate and ask questions.

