12.3 Recruitment Materials: n/a

12.4 Payment: n/a

### **13.0 Withdrawal of Participants**

13.1 Withdrawal Circumstances: Subjects who have consented prior to the day of surgery and for some reason choose not to participate will be withdrawn and a notation will be made in the study records and these people will be considered screen failures. The surgeon may choose to withdraw the patient from the study prior to surgery for any medical reason or if they suffer a major life threatening adverse event.

13.2 Withdrawal Procedures: If the patient is withdrawn from study prior to the procedure, they will be noted in study records as screen failures. If they undergo the procedure and they decide they no longer want to be a part of the study or withdrawn by the physician, they will be withdrawn and no further data will be collected. This will also be noted in the study documentation.

13.3 Termination Procedures: If the study is terminated for any reason, or there is more than 5 % major adverse events the data that is already collected will be stored in a secure location only accessible to research personnel on this study. No further data will be collected if the study is terminated. Risks to Participants

13.4 Foreseeable Risks: There is a risk of loss of privacy as well as inconvenience the patient as we will ultrasound them prior to and after surgery. Otherwise this is a minimal risk study

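### Eligibility does not use the pre-block scan, so patients whose hemidiaphragm is already weak or cannot be imaged can be randomised, and the plan does not say how they count

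*Combined protocol and SAP*

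**What the plan says.** Section 9.2 gives the whole exclusion list: "Exclusion Criteria: Non-English speaking patients". The inclusion criteria in 9.1 concern age, shoulder surgery with an interscalene block, and length of stay. Neither mentions the diaphragm, the phrenic nerve or image quality.

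Section 6.1 adds a route for patients outside the two parent studies: "If the patient is not enrolled or does not fit inclusion criteria for the RCR or TSA study they will then be randomized". Whatever those studies exclude, their criteria do not filter everyone who enters here.

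Under the same section, patients "have an ultrasound examination of their diaphragm at baseline prior to the block". No section says what follows if that scan shows little movement or gives no usable image. The only related provision is in 13.1: "The surgeon may choose to withdraw the patient from the study prior to surgery for any medical reason".

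On the outcome, section 4.1 says "The primary study endpoint will be diaphragm excursion (movement in cm) from rest to sigh in a sitting position". Section 15.1 asks the statistician "to evaluate for differences (if any) between the movement of the diaphragms in each group" and names no baseline adjustment. Block as an outcome rate appears only in the power analysis of 15.2: "We assumed a 5% rate of block at 24 hours in bupivacaine and a 66% block for liposome bupivacaine". No cut-off is given there, no reference to the patient's own baseline, and no rule for a scan that cannot be read.

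**The concern.** The trial asks how far the block stops the hemidiaphragm moving. A patient whose hemidiaphragm (taken here as the one on the operative side) barely moves before the block cannot answer that, because low movement at 24 hours may owe nothing to the block. A patient who cannot be imaged has no primary endpoint at all. The plan randomises both kinds of patient and leaves their handling open.

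The sample is small enough for this to matter. Randomisation balances such patients only on average, and with 9 evaluable per group one patient is 11 percentage points of an arm (1/9). The scan that would identify them is already scheduled, so the information is collected but not used for eligibility. If handling is settled after the data are seen, the choice can also affect the result.

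**Working it through.** **Inputs.** From 15.2: block at 24 hours 5% (bupivacaine) and 66% (liposome bupivacaine), alpha 0.05, power 80%, 9 per group, 22 enrolled. Two-sided testing is assumed, since 15.2 does not state it. The share q of patients already weak or unmeasurable is not in the documents. Values of 2%, 5% and 10% are assumed to show the range.

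**The plan's own figure.** Two proportions, pooled variance, no continuity correction, mean rate (0.05 + 0.66)/2 = 0.355:

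n = [1.96 × √(2 × 0.355 × 0.645) + 0.842 × √(0.05 × 0.95 + 0.66 × 0.34)]² / 0.61² = 8.4, rounded up to 9.

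This reproduces "With an alpha of 0.05 and power of 80% we determined we need 9 patients in each group". Normal-approximation power at 9 per group is 83%.

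**Exact power.** For each pair of counts out of 9, multiply the two binomial probabilities and sum over the pairs that favour a higher rate on liposome bupivacaine with p ≤ 0.05. This was done for the uncorrected Pearson chi-square and for Fisher's exact test. At q = 0 the result is 88%/73%. That Fisher power is already below 80% is a separate matter; these figures serve only as the reference.

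**Three readings of an affected patient.**

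- Counted as blocked (absolute excursion): the rate becomes q + (1 − q)p in each arm.
- Counted as not blocked (fall from own baseline, little room to fall): the rate becomes (1 − q)p.
- Missing: the rates stand, but one patient per arm is lost, giving 8 v 8.

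| q | Rates if blocked | Pearson/Fisher | Rates if not blocked | Pearson/Fisher |
|---|---|---|---|---|
| 0 | 5% v 66% | 88%/73% | 5% v 66% | 88%/73% |
| 2% | 6.9% v 66.7% | 85%/70% | 4.9% v 64.7% | 86%/71% |
| 5% | 9.8% v 67.7% | 79%/64% | 4.8% v 62.7% | 84%/67% |
| 10% | 14.5% v 69.4% | 71%/55% | 4.5% v 59.4% | 80%/61% |

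Missing, 8 v 8: 83%/62%.

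**One patient.** Suppose an affected patient counts as blocked and falls in the bupivacaine arm, turning 0/9 into 1/9. The liposome count needed for Fisher p < 0.05 rises from 5/9 (p = 0.029) to 6/9 (p = 0.0498). At a true 66% the chance of reaching it falls from 84% to 63%. Under the same scoring, one affected patient in the liposome arm raises Fisher power from 73% to 80%. One patient can thus move the result either way.

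**How likely is at least one?** In a 9-patient arm, 1 − (1 − q)^9 is 17%, 37% and 61% at q = 2%, 5% and 10%. Among all 22, 1 − (1 − q)^22 is 36%, 68% and 90%.

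**The case against.** A reader might infer that these patients would be scored as blocked in either arm, and so take the drop to 79%/64% or 71%/55% as the demonstrated loss. The documents do not support that. The primary endpoint is continuous, block has no definition, and a scan without an image is missing data rather than zero movement. If block meant a fall from the patient's own baseline, a weak baseline would tend to count as not blocked, and Pearson power would stay at 80% or more up to q = 10%. Nor does anything in the documents make a q of 5% to 10% more plausible than 1% or 2%. This objection stands, and it is why all three readings are shown.

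It can also be said that safeguards exist. The surgeon may withdraw a patient before surgery, 40 patients are consented to reach 22, 15.2 allows 20% for drop-out, screen failure and early discharge, and the parent studies may have exclusions not visible here. These help only in part. The withdrawal power is discretionary and not tied to the scan, the allowance replaces numbers without saying who is ineligible, and 6.1 admits patients who fail the parent criteria.

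A further argument is that baseline adjustment alone would deal with weak baselines without narrowing the population. It would help and belongs in the fix, but 15.1 does not specify it, and it cannot recover a patient with no usable baseline image.

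Finally, a reader might want to exclude dysfunction on either side on safety grounds. The documents give no figure for that risk, and the non-operative side is not linked to the measured endpoint.

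**Conclusion.** The point holds as a gap in eligibility and handling. It is certain from the text that language is the only exclusion, that patients failing the parent criteria are randomised here, and that the pre-block scan decides nothing. The consequence is that patients with an uninformative or unmeasurable primary endpoint can enter, and their classification is open.

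The size is conditional. It rests on the assumed q, on two-sided testing of the binary contrast in 15.2 rather than on the continuous endpoint, and on 9 evaluable per group. Against 88%/73%, the loss at q = 2% is about 2 to 3 points under either scoring. At q = 10% it is 17 to 18 points if these patients count as blocked, and 8 (Pearson) to 12 (Fisher) points if they do not. Losing one patient per arm costs 5 (Pearson) to 11 (Fisher) points. No single figure is the plan's actual loss. The change is worth making because it is cheap and the trial is small.

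**What to change.** Add to 9.2 an exclusion for known phrenic-nerve or diaphragm dysfunction on the operative side, and for a pre-block operative-side sigh scan that is not measurable or is below a minimum excursion in cm. The investigators should set that minimum in advance.

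Apply it at the existing baseline scan. For patients randomised here, this comes before randomisation. For parent-study patients, who are already allocated, it comes before the block and is judged by someone unaware of the allocation. Record these patients as screen failures, not as part of the 22.

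In 15.1, state that the 24-hour comparison of excursion is adjusted for baseline excursion, for example by ANCOVA. If a block rate is reported, define it, including its relation to the patient's own baseline and the handling of unreadable scans.

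The cost is one amended criterion and a short addition to the analysis plan. No extra scan is needed. A few candidates are lost and the population is slightly narrower; the centre reports about 500 shoulder procedures a year. Whether contralateral dysfunction should also exclude a patient is a clinical question for the investigators.
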